5.2 Secondary Aims

5.2.1 Aim 1

To implement a multicenter lumbar CSF catheter study employing standardized methodology and SILK™ technology. The following criteria will be evaluated as outcomes to determine feasibility:

Enrollment comparisons of research subjects at each of the 5 sites. Screen failure rates will be evaluated by cause, by number and by site. Demographics will be described across sites. There will be comparison of protocol deviations and sampling results between the sites. Adequacy of sample collections to permit analyses of PK and PD effects of Posiphen during the SILK will be tabulated. Description of the adequacy of SILK sampling, Pk and PD during the confinement visits will be undertaken with comparisons across sites.

Research Satisfaction Questionnaires: Descriptive ratings of participants in response to the research study will be undertaken across visits including baseline and post-confinement when this questionnaire was administered. The responses on the survey will be grouped and compared to address the experience across the trial with characterization of the most frequent terms. Cross tabulations and shift tables will be used to address the response to the SILK procedure through its categorical variables and its influence on participant satisfaction. We will explore whether there is any indication of an effect of treatment on these participant profiles.

5.2.2 Aim 2

To assess the PD effects of treatment with Posiphen versus placebo on the levels of the following biomarkers in CSF of subjects with early AD: Ab 38 and 40, sAPPa, sAPPb, total tau protein.

Mean changes in these biomarkers will be compared across treatment arms between baseline and day 21 time 0 prior to the leucine infusion pooling all participants treated with Posiphen vs placebo across cohorts. Linear regression modelling will allow the comparison of mean change scores in the analytes between the active and placebo groups while adjusting for covariates including age, gender, MMSE at baseline, and Apo-e status as well as armcode and dose cohort and cohort-by-armcode interaction.

To evaluate the PK PD relationships, trough levels of Posiphen at day 21 (time 0) will be examined as a predictor of change in the CSF levels of each of these biomarkers between baseline and day 21. A linear regression model will be used to predict the change in CSF analyte with the covariates of trough PK, age, and gender. Other PK measures will be similarly evaluated including AUC, and Cmax.

In a secondary analysis to evaluate the effect of dose, we will use a similar regression model with terms for placebo and each dose group as predictors, including age and gender as covariates.

5.2.3 Aim 3

To assess whether there are short-term cognitive and/or neuropsychiatric effects of Posiphen in subjects with early AD, either positive or negative on ADAS-Cog12, MMSE, Neuropsychiatric Inventory (NPI).

These cognitive and neuropsychiatric measures will be compared between Posiphen and placebo using multiple linear regression. This methodology will allow the comparison of mean change scores between the active and placebo groups while initially adjusting for covariates; age, gender, treatment arm and baseline MMSE. Dose effects will be assessed as part of this analysis to investigate trends. The effects of ApoE genotype on these clinical outcome measures will also be explored as a tertiary analysis.

C2N will analyze Beta Amyloid 38 (Ab38), Ab40, and Ab42. The ADCS Biomarker Core will analyze Soluble Amyloid Precursor Protein alpha (sAPP α), Soluble Amyloid Precursor Protein alpha (sAPP β), and total Tau protein.

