Posiphen is thought to act at the 5'UTR of the APP mRNA and lowers APP and A β protein levels in animal models, and decreased sAPP levels in human CSF. Preliminary data suggests that these effects are achieved via the same mechanism of binding to the 5'UTR of mRNAs and inhibiting their translation.

As Posiphen is thought to inhibit the synthesis of APP, as well as other neurotoxic aggregating proteins, it might have a broader spectrum of activity and protect neurons and have a disease-modifying effect in AD as well as other neurodegenerative disorders.

CSF Sampling and SILK™

Sampling CSF repeatedly for as long as 36 hours through a lumbar catheter had been initially used in a few studies related to AD treatment during the 1990s ([Cutler 1998](#)). The technique has gained greater utility in relation to measuring pharmacological effects on A β with the addition of SILK™, a technique developed by Dr. R. Bateman and colleagues at Washington University ([Bateman 2006](#)). This technique involves placement of a lumbar CSF catheter, followed by intravenous infusion of $^{13}\text{C}_6$ -labeled “heavy” leucine for 9 hours. Leucine is an essential amino acid that undergoes active transport into the brain. $^{13}\text{C}_6$ leucine is non-radioactive, harmless to humans and the environment, and is physically identical to unlabeled ($^{12}\text{C}_6$) leucine except for an additional proton difference in the mass of the amino acids. The leucine is incorporated into a fraction of newly synthesized proteins throughout the body, including the brain, which are secreted into the CSF. Samples of CSF are collected and A β is immune-precipitated from the CSF, and the ratio of A β containing $^{13}\text{C}_6$ -leucine to that containing unlabeled leucine is measured using mass spectrometry. During hours 4-12 after start of the leucine infusion, the fraction of labeled A β in the lumbar CSF increases, reaching a maximum of about 10%. The slope (change in % labeled A β /time) is called the fractional synthesis rate (FSR) and is a measure of the rate of A β synthesis in the brain. During late stages of the catheter procedure (hours 24-36), the fractional % of A β that is labeled decreases linearly, and the slope is measured to calculate the fractional clearance rate (FCR). Using this method, Bateman and colleagues estimated that A β has a rapid FSR and FCR in CSF.

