Power estimates for SILK™ studies involving measurements of FSR of Ab40 were determined by analysis of data provided by C2N, Inc., and modeled to evaluate a primary analytic goal of demonstrating a monotonic dose response relationship to Posiphen treatment. Based on a two-sided t-test for the difference between two independent means at a significance level (alpha) of 0.05 and a statistical power of 80% (1-beta), a sample size of 5 subjects in each treatment group (n active = 15) and 9 controls will provide at least 80% statistical power to detect a 27% change in the mean Ab40 FSR. The following table provides estimated power analysis to detect different effect size reductions of FSR Ab40 of 27% with 2-sided alpha and significance set at 0.05, assuming no dropouts during the SILK™ study:

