The primary outcome measure of Fractional Synthesis Rate (FSR) of Abeta 40 will be compared across all Posiphen treated groups to placebo. A linear regression model will be used to evaluate treatment effects on the FSR Abeta 40, with age and gender as covariates. Quality control of samples for the FSR 40 will be ascertained to determine sufficiency of the sample values prior to this regression analysis.

A secondary analysis will test for possible dose group by treatment interaction.

Exploratory analyses will include PK AUC correlation to Abeta 40 FSR and other SILK measured analytes (Abeta 38, 42, ratio 42/40, total Abeta peptides) including absolute synthesis and clearance.

C2N will analyze Beta Amyloid 40 (Ab40).

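### CSF biomarker change scores are to be compared without the analyte's own baseline and on no stated scale, and no percentage effect with a confidence interval is planned for these biomarkers or for Aβ40 FSR

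*SAP*

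**What the plan says.** SAP 5.2.2 covers the CSF levels of Aβ38, Aβ40, sAPPα, sAPPβ and total tau (Aim 5 in the protocol). It compares change from baseline to day 21, time 0: "Linear regression modelling will allow the comparison of mean change scores in the analytes between the active and placebo groups". The named covariates are age, gender, baseline MMSE, ApoE status, arm, dose cohort and cohort-by-arm interaction. The analyte's own starting level is not among them. No log, ratio or percentage scale is named.

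For the primary PD outcome, SAP 5.1.3 says "A linear regression model will be used to evaluate treatment effects on the FSR Abeta 40, with age and gender as covariates". Protocol 6.5 gives ANOVA. Neither names a transformation, a percentage effect or a confidence interval.

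The sizing statement in SAP section 4 is a percentage: the design "will provide at least 80% statistical power to detect a 27% change in the mean Ab40 FSR". It rests on a "two-sided t-test for the difference between two independent means at a significance level (alpha) of 0.05".

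The SAP asks for a 95% CI and a geometric mean with %CV only for PK parameters (5.1.2).

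**The concern.** Two things are at stake.

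**Precision for the CSF levels.** A change score is follow-up minus baseline, so measurement error in the baseline enters it with a negative sign and the score is correlated with baseline. If the drug effect is also proportional, the expected change grows with the starting level. Either way, a model without the analyte's baseline leaves removable variance in the residual and leaves the estimate exposed to chance baseline differences between 15 and 9 subjects. MMSE and ApoE do not stand in for it.

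**A result that can be read against the design.** The trial was sized on a 27% change, but the plan does not commit to a percentage effect with its uncertainty. With the scale left open, the choice between raw change, percentage change and log ratio could be made after the data are seen.

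**Working it through.** **1. The plan's own power figure**

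Inputs from SAP section 4: two-sided α = 0.05, a 27% change, and "a sample size of 5 subjects in each treatment group (n active = 15) and 9 controls". The SD is not given; the estimates "were determined by analysis of data provided by C2N, Inc". It was therefore back-solved from the 0.851 cell.

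- Noncentrality = d × √(15 × 9 / 24) = 1.324 × 2.372 = 3.140, with 22 df and critical t 2.074. Power = 0.851.
- The same d = 1.324 reproduces all nine cells within 0.001.
- Implied SD = 0.27 / 1.324 = 20.4% of the placebo mean. Read as a ratio of 0.73, the implied log-SD is 0.3147 / 1.324 = 0.238.

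The table is sound.

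**2. FSR: does the scale matter for power?**

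Simulated lognormal FSR, 27% fall, 15 versus 9:

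| CV | Raw | Log |
|---|---|---|
| 20% | 0.949 | 0.949 |
| 25% | 0.826 | 0.824 |
| 30% | 0.680 | 0.679 |

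It does not. (At CV 20% these values exceed 0.851 because in the simulation the active-arm SD shrinks with its mean, whereas the plan's t-test assumes a common SD.)

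**3. FSR: what the percentage report would look like**

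If the observed fall were 27%, with √(1/15 + 1/9) = 0.4216:

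- Log scale: −0.3147 ± 2.074 × 0.238 × 0.4216 = −0.3147 ± 0.208. Back-transformed, the fall is about 10% to 41%.
- Raw difference over a placebo mean treated as fixed: 27% ± 2.074 × 20.4% × 0.4216 = 27% ± 17.8%, about 9% to 45%.

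**4. CSF levels: baseline and scale**

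The documents give no CV or error model, so these are assumptions: lognormal levels, multiplicative error and a proportional effect, 15 versus 9. The baseline-adjusted column used 3,000 runs (Monte Carlo error about 1 point); the others used 20,000.

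| Between-subject CV | CV of log ratio | Fall | Raw change | Raw change + baseline | Log ratio |
|---|---|---|---|---|---|
| 30% | 20% | 0 | 0.049 | 0.048 | 0.050 |
| 30% | 20% | 15% | 0.406 | 0.460 | 0.465 |
| 40% | 10% | 15% | 0.878 | 0.919 | 0.960 |
| 40% | 20% | 15% | 0.386 | 0.433 | 0.466 |
| 60% | 10% | 15% | 0.801 | 0.871 | 0.955 |
| 60% | 20% | 15% | 0.337 | 0.390 | 0.460 |

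In these rows the baseline covariate alone adds 4.1 (0.919 − 0.878) to 7.0 points (0.871 − 0.801). For a 27% fall with log-ratio CV 20% it adds 7.9 (0.948 − 0.869) to 12.8 (0.890 − 0.762). Type I error stays near 5%.

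**5. What if error is additive?**

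Further simulations with a 15% fall used both error structures.

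- Baseline covariate alone, against unadjusted raw change: roughly 3 to 10 points gained under either structure.
- Log model with log baseline, against unadjusted raw change: roughly 5 to 18 points gained under multiplicative error.
- Log model with log baseline, against raw change already adjusted for baseline: about +1 to +11 points under multiplicative error, but about −4 to −26 under additive error.
- One setting without baseline adjustment (between-subject CV 40%, additive error 10%): raw change 0.62, log ratio 0.50.

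The benefit of the baseline covariate is robust. The benefit of the log scale depends on the error structure.

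**The case against.** **The FSR analysis is not wrong.** Regression on FSR targets the quantity the trial was sized on, and a percentage can be obtained by dividing the coefficient by the placebo mean. This stands. What remains for FSR is a reporting gap: the plan does not commit to that percentage or its interval.

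**The 27% does not carry over to the CSF levels.** A reader might infer that the documents predict a proportional fall in every analyte. They do not. The 27% is stated for Aβ40 FSR only. The phrase "inhibiting their translation" (Protocol section 4) is a mechanism statement offered as preliminary and is silent on scale. The reduction of up to 60% (Protocol 3.1) is in mouse brain, and the human CSF finding (Protocol 3.2) carries no percentage. Proportionality is a plausible inference, no more.

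**High-baseline subjects do not dominate.** That too is a tempting reading of raw change scores. Under the assumed CVs, the four highest of 15 active subjects (27%) carry 33% to 46% of the summed expected fall. That is extra weight, with some loss of power and no type I inflation.

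**The SAP is silent on scale rather than committed to raw units**, and its covariate list is worded openly enough to admit more terms. Both are true. Raw units are only the default reading, and an unnamed covariate is not pre-specified.

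**The simulations are not the SAP model.** They carry at most one extra covariate, whereas SAP 5.2.2 lists several plus an interaction. The absolute powers should not be read as those of the planned analysis; the comparisons between models are what matter.

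**Conclusion.** The point holds as a gap in specification and precision. SAP 5.2.2 omits the most useful covariate for a change score and names no scale, and neither PD section plans a percentage effect with a CI.

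For a 15% fall, the baseline covariate is worth roughly 3 to 10 points of power under either error structure. The log model with log baseline is worth roughly 5 to 18 points over the unadjusted change score if error is multiplicative. These sizes rest on assumed between-subject CVs of 20% to 60% and error CVs of about 10% to 20%, none of which is in the documents.

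For FSR there is no power loss to recover. The planned comparisons keep their type I error, and the power table and N = 24 stand.

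**What to change.** In SAP 5.2.2:

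- Add each analyte's baseline value to the model, defined as the screening CSF level. Protocol 12.2.1 already provides for Aβ, sAPP and tau analyses on that sample. For consistency, do the same in the dose-group and PK–PD models of that section.
- Pre-specify log level with log baseline as covariate. Report the Posiphen:placebo geometric mean ratio as a percentage change with 95% CI.
- Give the baseline-adjusted raw-unit analysis as a sensitivity analysis.

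In SAP 5.1.3:

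- Report the Aβ40 FSR effect as a percentage of placebo with 95% CI. Regression on log FSR is one convenient route, with the same power. If the raw scale is kept, state how the interval for the percentage is formed.

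Cost: a few lines of SAP text, one model degree of freedom per analyte, and no extra subjects or samples. Results will read as ratios rather than concentration differences. If assay error proves additive, the log scale can lose power, which is why the raw-unit sensitivity analysis should be named in advance.

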6.3 Safety and Tolerability Analysis

Safety and tolerability will be assessed with physical examinations, vital signs, clinical laboratory values, use of concomitant medications, and AE reports. The frequencies of adverse events, serious adverse events and laboratory abnormalities between the participants across the three groups will be compared. The severity of cholinergic adverse events will be carefully evaluated taking the criteria in Appendix 5 into consideration (modified from Common Terminology Criteria for Adverse Events (CTCAE) version 4.03) as there is potential for an interaction between Posiphen and Donepezil through the inhibition of AChE, thereby resulting in increased cholinergic activity.

Each dose group will be completed and evaluated for safety and tolerability by the standing ADCS DSMB before the next dose group is initiated. Drug administration at the next higher dose level may not proceed until written confirmation is provided from the ADCS DSMB indicating that the results of the previous dose level were evaluated and that it is permissible to proceed to a higher dose level.

Subjects who do not tolerate study drug during the initial 3-week at-home treatment period will be discontinued and replaced by new subjects. If two subjects at a given dose are discontinued due to adverse events, no additional subjects will be added at this dose level until a safety review has been conducted. The ADCS DSMB will determine the appropriate dose level for additional subjects. The ADCS DSMB has the option to change the allocation of future patients to active drug versus placebo based on statistical advice to maintain an appropriate balance between placebo subjects and subjects on active drug.

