9.3 Baseline Visit

Baseline procedures include cognitive assessments, behavioral assessments, Research Satisfaction Survey, safety assessments, and review of concurrent medications and adverse events that occur in clinic.

For a complete list of all visit procedures, refer to the Schedule of Events (Appendix 1).

Following completion of all baseline procedures, subjects who continue to meet all protocol inclusion criteria and no exclusion criteria, should be scheduled for the confinement visit. The person should then be randomized, dispensed study drug and instructed on proper storage and dosing. The subject should be instructed on 1) when to take the first dose of the study drug and 2) the duration of study drug administration (21-23 days at home) based on the scheduled date of the confinement visit.

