12.2 Biofluids

12.2.1 CSF for Biomarkers

Standard Lumbar Puncture:

A lumbar puncture will be performed as part of the screening visit, in the morning (before 10am is recommended), after an overnight fast. 2ml CSF will be sent for analysis by the site (total protein, glucose, cell count) to a local lab. The remaining CSF will be placed into a 14 ml conical polypropylene tube, inverted gently 3-4 times, then centrifuged at 1500 x g for 10 minutes at room temperature. The supernatant should be aliquoted into 2.0 ml tubes, frozen at -80°, and shipped overnight to the ADCS Biomarker Core. The ADCS Biomarker Core will subsequently send these samples to C2N for processing and analysis according to Biomarker core SOPs. Analyses will include AD biomarkers (e.g., A β , sAPPs, tau).

CSF samples will be banked in the biospecimen repository of the ADCS Biomarker Core for various future research studies; access to samples will be granted according to SOPs established by ADCS Biomarker Core.

Prior to the LP, a coagulation panel will be obtained to rule out a clotting disorder. Participants taking an anti-platelet agent (e.g., Plavix) must be discontinued from that agent for a minimum of 5 days prior to the lumbar puncture. These participants may continue with the agent after a minimum of 24 hours post LP. Participants who are taking anticoagulants (e.g., warfarin (Coumadin) and/or dabigatran (Pradaxa) may not undergo an LP and are not suitable to participate in this study.

When done at the same visit, the LP should occur after the MRI scan. When done at the same visit, if the MRI scan can only be scheduled prior to the LP, the site must contact ADCS Clinical Operations for permission before proceeding. In the unplanned event that the MRI does not precede the LP, there should be a minimum window of 72 hours between the MRI and the LP. LP under fluoroscopy is permitted; however, the site must contact ADCS Clinical Operations for permission before proceeding. Site personnel should advise the subject that use of fluoroscopy (x-rays) involves exposure to radiation.

Each study participant or a person designated to speak for them will be contacted by phone approximately 24 hours after the LP to confirm participant well-being and any adverse events.

CSF Sampling:

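### The change-score models for the CSF biomarkers (SAP 5.2.2) and for ADAS-Cog12 and NPI (SAP 5.2.3) do not prespecify the outcome's own baseline as a covariate.

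*SAP*

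**What the plan says.** SAP 5.2.2 takes as response the change in each CSF analyte from baseline to day 21, time 0, "pooling all participants treated with Posiphen vs placebo across cohorts". The linear model is described as "adjusting for covariates including age, gender, MMSE at baseline, and Apo-e status as well as armcode and dose cohort and cohort-by-armcode interaction". Two further regressions follow in the same section. One predicts the change from trough Posiphen level, age and gender, with AUC and Cmax handled in the same way. In the other, "we will use a similar regression model with terms for placebo and each dose group as predictors", again with age and gender. Neither lists the analyte's baseline.

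SAP 5.2.3 compares mean change in ADAS-Cog12, MMSE and NPI, "initially adjusting for covariates; age, gender, treatment arm and baseline MMSE". The MMSE model therefore has its own baseline; the ADAS-Cog12 and NPI models do not.

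The baseline values exist. For the screening lumbar puncture, Protocol 12.2.1 states "Analyses will include AD biomarkers", with Aβ, the sAPPs and tau as examples. Protocol 9.3 states "Baseline procedures include cognitive assessments, behavioral assessments", and the Schedule of Events places ADAS-Cog12 and NPI at that visit.

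For the primary outcome, SAP 5.1.3 keeps the interaction out of the main model: "A secondary analysis will test for possible dose group by treatment interaction".

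**The concern.** With 15 and 9 subjects, randomization leaves appreciable chance differences in baseline. A change score removes all of the baseline difference, which over-corrects whenever the correlation between baseline and follow-up is below 1. Part of any imbalance then reappears in the treatment estimate with the opposite sign. Baseline MMSE is not a substitute for baseline Aβ40, sAPP or tau.

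Because the plan does not say whether own baseline enters, the choice could be made after the data are seen. The two estimates can differ visibly in a sample this small.

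A smaller gap sits in the same 5.2.2 model. It contains a cohort-by-arm interaction, but the SAP neither defines armcode nor names the contrast that yields the pooled effect.

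**Working it through.** **The plan's own figure.** The only power figure is for Aβ40 FSR: 0.851 for 15 active and 9 controls, 27% change, two-sided 0.05 (SAP 4.1). The SD is not stated. A noncentral t calculation gives 0.851 at a standardized difference of 1.324 (SD 27/1.324 = 20.4% of the mean), and the other eight table cells then agree within 0.001. No power figure is given for the secondary biomarkers, so 1.324 is used below only as a yardstick.

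**Chance imbalance.** In baseline SD units, the SE of the baseline difference is √(1/15 + 1/9) = 0.422. For normal baselines, P(|difference| > 0.5) = P(|Z| > 0.5/0.422 = 1.186) = 0.24. With equal SDs at both times, a baseline difference D shifts the unadjusted change-score estimate by (1 − r)·D in size. For D = 0.5 this is 0.25 SD at r = 0.5, 0.15 at r = 0.7 and 0.05 at r = 0.9.

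**Precision.** Three factors act on the confidence interval:

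- Residual variance, baseline-adjusted over change score: (1 − r²)/[2(1 − r)] = (1 + r)/2.
- Estimating one more slope: expected variance inflation 1 + 1/(f − 1), where f is the residual df after adding baseline.
- A larger t quantile from losing 1 df.

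For 5.2.2 with 24 subjects, the parameters are intercept, arm, 2 cohort, 2 interaction and 4 covariates (ApoE coded with 1 df). That is 10, so residual df go from 14 to 13. For 5.2.3 there are 5 parameters, so df go from 19 to 18.

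CI width ratio = √[(1 + r)/2] × k, where

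- 5.2.2: k = √(1 + 1/12) × (2.1604/2.1448) = 1.048
- 5.2.3: k = √(1 + 1/17) × (2.1009/2.0930) = 1.033

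| r (assumed) | √[(1+r)/2] | 5.2.2 | 5.2.3 |
|---|---|---|---|
| 0.5 | 0.866 | 0.908 | 0.894 |
| 0.7 | 0.922 | 0.967 | 0.952 |
| 0.85 | 0.962 | 1.008 | 0.993 |
| 0.9 | 0.975 | 1.022 | 1.007 |
| 0.95 | 0.987 | 1.035 | 1.020 |

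The table takes the listed covariates as unrelated to the outcome's baseline. Where they predict it, the gain shrinks. In simulation at r = 0.5, the SE ratio for 5.2.2 (arm and cohort main effects) moves from 0.898 to 0.932 if the covariates explain 30% of baseline. For 5.2.3 it moves from 0.891 to 0.971 if the scale correlates −0.8 with MMSE.

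**Interaction.** In the planned 3 × (5 + 3) design, the equal-weight average of the three cohort effects has SE 0.422 residual SD, the same as the arm effect without the interaction. The cost of the term is 2 df (14 against 16). Simulated with four covariates and a mean effect of 1.324, removing the term changes the CI width as follows:

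- equal effects at all doses: about 2.5% narrower (power about 0.74 with the term, 0.76 without)
- effects in ratio 1:2:3: about 1% wider
- effects in ratio 0:1:2: about 12% wider (power 0.72 falls to 0.64)

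If cells become unequal, the weighting matters. With a third cohort of 2 active and 1 placebo (illustrative), the SE is 0.534 with equal weights and 0.476 weighted by active numbers.

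**The case against.** The strongest reply is that the benefit is uncertain. The 5.2.2 list is introduced as open, the omission causes no bias over randomization, and the gain rests on a correlation the documents do not give. At r of about 0.85 or more, adjustment gains nothing or costs a little precision, and those are also the values at which chance imbalance does least harm. All of that stands, and it limits the size of the point.

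It does not remove the point. The 5.2.2 baseline comes from a screening puncture up to 42 days before the baseline visit, or from another study's puncture up to 90 days before it (Protocol 9.2 and 9.2.1). Follow-up is a catheter sample about three weeks into dosing, so a very high r should not be presumed. The covariate needs no new data and creates no further missing values.

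A reader might infer that the interaction makes the 5.2.2 analysis wrong. If armcode has two levels, R's default arm coefficient would be one cohort's 5-against-3 effect, with SE 0.730 against 0.422, or 1.73 times larger. The documents do not support that reading as the planned analysis: the SAP states the pooled target in words, and reporting a single-cohort coefficient would contradict it. It is a risk of mis-execution only.

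A reader might also infer that the term should be dropped because dose has its own model. That model uses a single placebo term, whereas the interaction compares each dose with its own cohort's placebo. Dropping the term helps only when effects are similar across doses, and this is an ascending-dose trial.

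**Conclusion.** The point holds as a gap in prespecification, for secondary outcomes only. The plan does not say that own baseline enters the 5.2.2 change models or the ADAS-Cog12 and NPI models of 5.2.3. It would go too far to say that the plan excludes it in 5.2.2 or that the randomized comparison is biased.

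The size depends on r. Adjustment is worth roughly 9–11% of CI width at r = 0.5 and 3–5% at 0.7, nothing at about 0.85, and costs 2–3.5% at 0.95. It also protects against an imbalance above 0.5 SD that has a 0.24 chance of arising. These figures assume 15 against 9 subjects, equal SDs at both times, normal baselines and listed covariates unrelated to baseline; the gain is smaller where those covariates predict it.

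The missing contrast is a minor clarification. The primary FSR model and the sample size are untouched.

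**What to change.** 1. In SAP 5.2.2, add the analyte's own baseline as a prespecified covariate in the pooled model, the dose-group model and the PK/PD change models, so that the same change score is adjusted consistently throughout.
2. In SAP 5.2.3, add baseline ADAS-Cog12 or baseline NPI to the matching model. The MMSE model needs no change.
3. As a clarification, if cohort-by-armcode stays in 5.2.2, define armcode as Posiphen versus placebo and name the equal-weight average of the three cohort effects as the pooled contrast. State that this weighting also applies if allocation changes, since under Protocol 6.3 "The ADCS DSMB has the option to change the allocation of future patients to active drug versus placebo". Removing the interaction is not recommended as the default.

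The cost is a few sentences of SAP text, settled before unblinding, and 1 df per model. No new data are needed. The downside is an interval up to about 3.5% wider if r is near 0.95.
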